## **6 SELECTION OF STUDY POPULATION**

Investigators should contact the Medical Monitor if they have questions about eligibility of specific subjects.

### **6.1 Inclusion Criteria**

Subjects will be eligible to participate in this study if they meet all of the following criteria:

1. Subject has provided full written informed consent prior to the performance of any protocol-specified procedure; or if unable to provide informed consent due to cognitive status, subject has provided assent and a legally authorized representative has provided full written informed consent on behalf of the subject.
2. Caregiver has provided full written informed consent, on a separate informed consent form (ICF), on his/her own behalf prior to the performance of any protocol-specified procedure.

3. Male and female subjects must be 55 years to 80 years of age, at the time of consent.
4. Subject has probable AD dementia according to the NIA-AA criteria ([McKhann 2011](#)) with clinical evidence of progressive cognitive decline in the last year. Clinical decline will be determined based on serial cognitive test scores, if available, or subject/caregiver report as documented by the Investigator.
5. Subject has an MMSE score between 12 and 24 inclusive at both screening and Visit 2 and a  $\leq 3$ -point difference between these visits.
6. Subject has a Modified Hachinski score  $\leq 4$  at screening.
7. Subject has brain MRI scan consistent with the diagnosis of AD performed during the screening period. Computed Tomography scan can be used only if the subject has an absolute contraindication for MRI.
8. Subject has a primary caregiver willing to accept responsibility for supervising the treatment (e.g., administering study drug), accompanying the study subject to clinic visits and assessing the condition of the subject throughout the study in accordance with all protocol requirements.
9. Subject is not likely to experience a change in living conditions (e.g., institutionalization, moving to a different city, etc.), or change in primary caregiver, during participation in the trial.
10. Subjects with background symptomatic therapy with acetylcholinesterase inhibitors, and/or memantine, are allowed as long as the dose has been stable for 90 days prior to screening and no changes are planned during the study.
11. Subjects who have occasional use of sedative agents are acceptable, but these agents should not be given within 48 hours prior to cognitive assessments.
12. Subjects who have background medications used for stable chronic illnesses that are not prohibited by the protocol are allowed. The dose of psychoactive drugs must be stable for 30 days prior to screening, and no changes must be planned during the study unless for safety reasons.
13. Subject has body mass index  $\leq 38$  kg/m^2 at Screening.
14. Subject must be able to ingest oral medications and can swallow the study drug without breaking or crushing.
15. Subject must be willing to undergo Apolipoprotein E genotype (ApoE) genetic testing (ApoE results may be disclosed after trial completion).
16. Subjects participating in the study must meet one of the following criteria:
  - a. Females: Surgically sterilized (e.g., hysterectomy, bilateral oophorectomy or tubal ligation) for at least 6 months or postmenopausal (postmenopausal females must have no menstrual bleeding for at least 1 year). If not postmenopausal, agree to use a highly effective method of contraception that can achieve a failure rate

of less than 1% per year when used consistently and correctly, such as hormonal contraception or a double barrier method (e.g., intrauterine device plus condom or true abstinence defined as in line with the preferred and usual lifestyle of the subject. Periodic abstinence e.g. calendar, ovulation, symptothermal, post-ovulation methods are not acceptable. Declaration of abstinence for the duration of a trial, and withdrawal are not acceptable methods of contraception) from 30 days prior to dosing until 30 days after last dose and have negative human chorionic gonadotropin ( $\beta$ -hCG) test for pregnancy at screening.

- b. Males who have not had a vasectomy must use appropriate contraception methods (barrier or true abstinence defined as in line with the preferred and usual lifestyle of the subject. Periodic abstinence e.g. calendar, ovulation, symptothermal, post-ovulation methods are not acceptable. Declaration of abstinence for the duration of a trial, and withdrawal are not acceptable methods of contraception) from 30 days prior to dosing until 90 days after last dose.

**Open Label Extension:** Subjects will be eligible to participate in the open label extension portion of the study if they meet inclusion criteria # 8, 9, 10, 11, 12, 14, and 16 above. Subjects with any change in their medical history that in the Investigator's opinion will increase the subject's risk of participating in the study or confounding study assessment should not continue in the open label extension portion of the study. The Investigator should contact the Sponsor with questions of eligibility for participation. **NOTE:** Effective 16 February 2021, the OLE portion of the study was terminated by the Sponsor.

## 6.2 Exclusion Criteria

Subjects will not be eligible to participate in this study if they meet any of the following exclusion criteria:

1. Subject has imaging consistent with other differential dementia diagnoses other than the diagnosis of AD. For example, any suggestion of vascular disease including multiple infarction involving large blood vessels or localized single infarction (angular gyrus, thalamus, anterior cerebral artery and posterior cerebral artery region), multiple lacunae of the basal nuclei or white matter or extensive lesions of the periventricular white matter or combination of several lesions are considered exclusionary. Additionally, any single lacune in an area known to impact cognition such as the hippocampus will also be exclusionary. Finally, Probable CAA with/without supporting pathological evidence according to the modified Boston criteria, if in the opinion of the investigator this may be contributing to symptoms overlapping with those of AD or confound neuropsychological assessments, would be exclusionary. Importantly, should there be any evidence of neurologic symptoms between scanning and baseline visits, rescanning is necessary to ensure proper patient selection.

2. Subject has had an increase or restoration of cognition based on medical history.
3. Subjects who meet the following imaging exclusion criteria will not be included in this study:
  - a. Claustrophobia that will result in significant anxiety and difficulty lying still for brain imaging (MRI or CT scan).
  - b. Severe motor problems or chronic pain indication that prevents the subject from lying still for brain imaging.
4. Subject with history of cancer requiring systemic therapy in the last 5 years; except for localized cancer of the skin and in-situ cervical cancer successfully treated with surgical excision. Stable (for at least 90 days) prostate cancer is allowed.
5. Subject has a contraindication for LP, such as infected skin over the needle entry site, possible increased intracranial pressure, severe thrombocytopenia or coagulopathy, suspected spinal epidural abscess, or spinal structural abnormalities that would interfere with LP procedures.
6. Subject has evidence of clinically significant unstable cardiovascular, pulmonary, renal, hepatic, gastrointestinal, neurologic or metabolic disease within 6 months prior to Screening.
7. Subject has any of the following cardiovascular conditions:
  - a. Unstable angina, uncompensated and/or symptomatic congestive heart failure (Grade 2 or higher on the New York Heart Association scale) or, myocardial infarction within 6 months.
  - b. Acute or poorly controlled blood pressure >180 mmHg systolic or >100 mmHg diastolic.
  - c. Current, or recent history of, any of the following that are clinically significant in the investigator's judgment: arrhythmia, hypotension, heart block (1st, 2nd or 3rd degree AV block), ANY bundle branch block, ventricular pacing, symptomatic ectopy, unstable arrhythmias including atrial fibrillation; stable atrial fibrillation is allowed.
  - d. History of prolonged QT or prolonged QT on screening ECG (QTcF  $\geq$ 480 msec).
  - e. History of prolonged PR interval or prolonged PR interval on screening ECG (PR >210 msec).
  - f. History of prolonged QRS interval or prolonged QRS interval on screening ECG (QRS >120 msec).
  - g. Supraventricular or ventricular ectopy on the screening ECG or Brugada pattern on the ECG.

8. Subject with major stroke, uncontrolled seizure disorder, or other medical illnesses that in the Investigator's opinion will increase the subject's risk of participation in the study or confound study assessments.
9. Subject with history or current evidence of major neurological or psychiatric illness such as schizophrenia, bipolar disorder, Parkinson's Disease, etc. Subjects with major depressive disorder that may interfere with the patient's ability to perform the study and all assessments. NOTE: Mild depression or depressive mood arising in the context of AD are not criteria for exclusion. The use of anti-depressants or the use of anti-epileptic medication for non-seizure-related treatment is allowed if the dose has remained stable for at least 60 days prior to enrollment.
10. Subject with history of violent or aggressive behavior that requires medication to control.
11. Subjects with active suicidal thoughts (Type 4 or 5 on the C-SSRS) in the 6 months preceding screening or at baseline; or have a history of a suicide attempt in the previous 2 years, or more than 1 lifetime suicide attempt; or are at serious suicide risk in the Investigator's clinical judgment.
12. Subject with history of alcohol or drug use disorder within 12 months of screening as defined by the Diagnostic and Statistical Manual of Mental Disorders-5.
13. Subject with previous treatment with investigational vaccine therapy for AD.
14. Subject has participated in another Investigational New Drug (IND) research study involving small molecule drugs within 60 days or biological drugs within 90 days prior to the first dose of study drug or 5 half-lives of the investigational drug, whichever is longer.
15. Subject has a history of epilepsy or seizure disorder requiring ongoing treatment, or any seizure or loss of consciousness within 6 months prior to enrollment.
16. Subject has any of the following laboratory findings at screening:
  - a. Alanine aminotransferase  $>3$  x upper limit of normal (ULN), aspartate aminotransferase  $>3$  x ULN, or history of clinically significant liver disease in the Investigator's judgment.  
**NOTE:** Subjects with ALT or AST  $>2$  x ULN at Visit 9/Week 40 will not be eligible to participate in OLE.  
**NOTE:** Effective 16 February 2021, the OLE portion of the study was terminated by the Sponsor.
  - b. Hemoglobin  $\leq 10$  g/dl.
  - c. International Normalized Ratio (INR)  $>1.5$  or total bilirubin  $>1.5$  x ULN (unless subject has evidence of Gilbert's disease).
  - d. Creatinine clearance (CL) of  $<45$  ml/min.
  - e. Poorly controlled diabetes as defined by hemoglobin A1c (HbA1c)  $>8$ .

- f. Positive blood screen for Human Immunodeficiency Virus (HIV 1 and 2), Hepatitis B surface antigen (HBsAg), or Hepatitis C virus antibodies (HCV-Ab) at Screening.
  - g. Positive urine screen for drugs of abuse that include opiates, cocaine, amphetamines, or barbiturates.
17. Subject has abnormal laboratory tests that suggest an alternate etiology for dementia, such as serum vitamin B12 deficiency, thyroid function abnormality, severe anemia, electrolyte abnormality, or positive syphilis serology. In these cases, the patient should be re-evaluated to determine if these potential causes of dementia have been addressed. Only if these causes have been ruled out as the cause of the dementia can the patient be enrolled.
18. Use of systemic (i.e., oral, intravenous, etc., but not topical) antibiotics in the last 60 days or history of recurrent infection that requires chronic or repeated courses of antibiotics.

**Open Label Extension:** Subjects will not be eligible to participate in open label extension portion of the study if they meet any of the following exclusion criteria # 1, 4, 6, 7, 8-12, 15, 16 a, b, c, d and e. Laboratory testing and ECG results from Visit 9 will be used to evaluate eligibility. Subjects with any change in their medical history that in the Investigator's opinion will increase the subject's risk of participating in the study or confounding study assessment should not continue in the open label extension portion of the study. The Investigator should contact the Sponsor with questions of eligibility for participation. **NOTE:** Effective 16 February 2021, the OLE portion of the study was terminated by the Sponsor.

### 6.3 Subject Restrictions

#### 6.3.1 Prior and Concomitant Medications

Subjects will not be allowed to use medications or combinations containing medications from prohibited classes during participation in the study (i.e., from Screening (Visit 1) through Safety Follow-up Visit 11 or Visit OLE-9 for subjects participating in OLE. Prohibited concomitant medication classes include: anticholinergics, CNS-penetrant antihistamines, and antipsychotics.

The use of prescribed benzodiazepines and sedatives/hypnotics are allowed during the study but should not be used 48 hours before any study visit with cognitive testing.

The use of prescribed acetyl cholinesterase inhibitors (e.g., donepezil, rivastigmine, etc.) or memantine is allowed during the study as long as the dose has been stable for at least 90 days prior to Screening and there are no plans to modify the dose or stop treatment during the study. Switching to a different drug in the same class is prohibited during the study.

The use of prescribed medication for stable chronic illnesses, including psychoactive drugs, is allowed during the study as long as the medication class is not prohibited,

the dose has been stable for at least 30 days prior to Screening, and there are no plans to modify the dose or stop treatment during the study. Starting new medication during participation in the study should be avoided, unless deemed necessary by the Investigator.

Systemic (i.e., oral, intravenous, etc., but not topical) antibiotics are prohibited in the last 60 days prior to Screening (Visit 1), or history of recurrent infection that requires chronic or repeated courses of antibiotics.

Patients requiring treatment with prophylactic antibiotics in order to undergo minimally invasive oral examination procedures (measurements of pocket depth, gingival margin and bleeding on probing) due to preexisting medical conditions such as artificial heart valve, history of rheumatic fever or recent (within a year) joint replacement surgery, or currently receiving immunosuppressive therapy are eligible to participate in the study; however, they should be excluded from participating in oral examinations.

The use of any over-the-counter medicinal products, including herbal and dietary supplements, are allowed unless, in the opinion of the Investigator, the administration of the over-the-counter medicinal product could affect the subject's safety or the results of the study.

All medications (including drug name, dose, and dose regimen) administered from 30 days prior to Visit 1 through the Safety Follow-up Visit (Visit 11) will be recorded in the source documents and on the Prior and Concomitant Medication electronic Case Report Form (eCRF).

## **7 STUDY VISITS**

The study will consist of 3 periods: Screening period up to 6 weeks, treatment period up to 48 weeks, and a safety follow-up period of 6 weeks. When feasible, study visits should be performed at the same time of day for the same subject.

### **7.1 Screening: Visit 1 (Day -42 to Day -1)**

During the screening period, the eligibility of subjects will be confirmed according to the Schedule of Evaluations in this protocol (see [Table 1](#)). The following evaluations will be performed at Screening in the following order as close as possible when feasible:

1. Obtain informed consent from subject, and caregiver informed consent signed by the primary caregiver;
2. Past medical history and confirmation of cognitive decline in the last 12 months;
3. Concomitant medications;
4. Inclusion/exclusion criteria for eligibility;
5. Modified Hachinski;
6. Columbia-Suicide Severity Rating Scale (C-SSRS);

7. Mini-Mental State Examination (MMSE). Subjects with MMSE score of 12-24, inclusive, will have the rest of their screening procedures performed or scheduled);
8. Alzheimer's Disease Assessment Scale-Cognitive Subscale 11 (ADAS-Cog 11);
9. Clinical Dementia Rating, Sum of Boxes (CDR-SB);
10. Winterlight Speech Assessment (only in English speaking (primary language subjects and only in the US and UK);
11. 12-lead electrocardiogram (ECG);
12. Weight;
13. Vital signs;
14. Full physical examination, including height and body mass index (BMI) calculation;
15. Urine drug screen;
16. Urine pregnancy test (women of child bearing potential only);
17. Blood/urine sample collection for:
  - a. Serology (Hepatitis C virus antibodies [HCV-Ab], Hepatitis B surface antigen [HBsAg], Human Immunodeficiency Virus [HIV] 1 and 2);
  - b. Apolipoprotein E (Apo E) genotyping;
  - c. Follicle stimulating hormone (FSH) for peri-menopausal (irregular menstrual periods) or post-menopausal (no menstrual period for >12 months) female subjects;
  - d. Vitamin B12
  - e. Thyroid function tests
  - f. Syphilis
  - g. Pregnancy test (only if urine pregnancy test is positive); and
  - h. Safety laboratory tests;
18. Saliva collection;
19. Oral examination and collection of oral biomarker samples (subgingival plaque [SGP] and buccal cell swabs) (only at selected sites); and
20. Magnetic resonance imaging (MRI) of the brain. Computed Tomography (CT) scans of the brain can be used instead of MRIs only in subjects who have an absolute contraindication for MRI.

Screening procedures can be done on multiple days if needed, with more invasive procedures done after other screening procedures are completed. A screen failure is any subject who signs the informed consent but does not qualify for the study or discontinues the study prior to randomization. A subject can be rescreened if the Principal Investigator thinks the subject may qualify for the study upon rescreening, and if the Medical Monitor agrees.

## **7.2 Study Treatment: Visit 2 (Day 0)**

Subjects who meet all of the eligibility criteria will be scheduled for Visit 2.

Note: To accommodate the logistics of performing the baseline LP procedure, a separate visit within 7 days prior to V2/Day 0 may be scheduled. At this visit,

baseline MMSE score will be verified, and the LP procedure will be performed. The remaining V2 assessments must be completed at Day 0, when the first dose of study drug will be administered.

The following evaluations will be performed at this visit in the following order or as close as possible when feasible:

1. MMSE;
2. Lumbar puncture to collect cerebrospinal fluid (CSF) may be conducted up to 7 days prior to other procedures listed below;
3. Inclusion/exclusion criteria to assess for continued eligibility.
4. ADAS-Cog 11;
5. Alzheimer's Disease Cooperative Study Group - Activities of Daily Living (ADCS-ADL);
6. CDR-SB;
7. Randomization;
8. Concomitant medications;
9. Symptom-based physical examination;
10. Vital signs;
11. Neuropsychiatric Inventory (NPI);
12. C-SSRS;
13. Urine drug screen;
14. Blood/urine sample collection:
  - a. Pharmacokinetics (PK): A pre-dose trough sample will be drawn immediately prior to the AM dose. The exact times of AM dosing and PK sample collections at the site will be documented.
  - b. Serum and whole blood (peripheral blood mononuclear cells [PBMCs]) for biomarkers; and
  - c. Safety laboratory tests;
15. Saliva collection;
16. Winterlight Speech Assessment (only in English speaking (primary language) subjects and only in the US and UK);
17. Adverse events;
18. Administer study drug at the site;
19. 12-lead ECG 1-1.5 hours post-dose;
20. Blood sample collection: Second PK blood draw 30 minutes to 4 hours post-dose; and
21. Dispense study drug.

A screen failure is any subject who signs the informed consent but does not qualify for the study or discontinues the study prior to randomization. A subject can be rescreened if the Principal Investigator thinks the subject may qualify for the study upon rescreening, and if the Medical Monitor agrees.

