
 
1. Visit 10/ET MRI will be done only in subjects who had a screening MRI performed and may be done up to 8 days prior to Visit 10/ET. CT scans of the brain can be used instead of MRIs, only in subjects who have an absolute contraindication for MRI.
 
2. Administer the first MMSE as early in the screening period as possible. MMSE score should be <math>\geq 12</math> and <math>\leq 24</math> at both screening and Visit 2, and a <math>\leq 3</math>-point difference between visits, for inclusion in the study.
 
3. Oral biomarker samples include subgingival plaque and buccal cell swabs (only at selected sites).
 
4. Subjects will have follow-up oral examinations at 24 and 48 weeks.
 
5. Visit 10/ET oral examinations may be completed up to 8 days prior to Visit 10 (or ET) when applicable.
 
6. Baseline (V2) LP must be done after the baseline MMSE score has been verified and subject's eligibility has been confirmed, and prior to the first dose of study drug. To allow flexibility of scheduling the LP procedure, the MMSE and then the LP may be performed up to 7 days prior to baseline V2. Likewise, the LP at Visit10/ET may be performed up to 7 days prior to the other visit procedures, even if the LP is outside the visit window. The LP procedures must be
 
																				

- performed as per SOC and site specific SOPs, if applicable (including imaging before and/or during the LP, if required).
7. A pre-dose trough sample will be drawn at all visits 2, 3, and 7 immediately prior to the AM dose, and the subject will then take their dose of study drug on-site. The exact times of AM dosing and PK sample collections at the site will be documented. A single post-dose sample will be drawn from each subject while on-site at the clinic per the following schedule: V2 30 minutes - 4 hours; V3 60 minutes ± 30 minutes; V7 2 hours ± 30 minutes; V9 3 hours ± 30 minutes; and V10/ET 4 hours ± 30 minutes.
  8. At visits when the subject takes their dose of study drug on-site, ECGs should be measured approximately 1-1.5 hours after dosing.
  9. At Visit 3 and Visit 7, ECGs will also be performed at trough (prior to dosing).

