### **11.3 Final Analysis**

#### **11.3.1 Analysis Populations**

- **Intent-To-Treat Population (ITT):** The ITT population will include all subjects who are randomized regardless of whether or not they took study drug. This population will serve as the basis for all efficacy analyses. When change from baseline is assessed, subjects will be included in the analysis only if both a baseline and a postbaseline measure are available.
- **The Per Protocol population (PP):** The PP population will include all ITT subjects who do not have any major protocol deviations that would affect efficacy (e.g., <80% treatment compliance, taking a prohibited medication). Major protocol deviations will be reviewed and determined prior to unblinding. The PP population will be used for supportive sensitivity analyses.
- **Safety Population:** The Safety population will include all subjects who receive at least one dose of study drug. Safety analyses will be performed using the Safety population, and subjects will be analyzed according to the treatment they actually receive.

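### Section 7.2 lists the baseline C-SSRS after randomisation, so a site that follows the list cannot apply the baseline part of exclusion 11 before allocation

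*Protocol*

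**What the plan says.** Section 7.2 introduces the Visit 2 list with "The following evaluations will be performed at this visit in the following order or as close as possible when feasible". Its order is MMSE (1), lumbar puncture (2), "Inclusion/exclusion criteria to assess for continued eligibility" (3), ADAS-Cog 11 (4), ADCS-ADL (5), CDR-SB (6) and "7. Randomization". After that come "8. Concomitant medications", the symptom-based examination (9), "10. Vital signs", the NPI (11), the C-SSRS (12) and the urine drug screen (13). The first dose is item 18. The same section lets the MMSE and the lumbar puncture take place up to 7 days earlier and requires everything else on Day 0.

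Exclusion 11 in section 6.2 covers "active suicidal thoughts (Type 4 or 5 on the C-SSRS) in the 6 months preceding screening or at baseline". Sections 5.2 and 8.4 reserve randomisation for subjects who satisfy all criteria. Table 1 footnote 6 says the baseline lumbar puncture comes after the subject's "eligibility has been confirmed, and prior to the first dose of study drug". Section 11.3.1 states: "The ITT population will include all subjects who are randomized regardless of whether or not they took study drug".

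**The concern.** Exclusion 11 has a limb that only the baseline C-SSRS can answer, and the Synopsis and section 4.1 equate baseline with Visit 2. In the listed order that result does not exist at the eligibility check or at randomisation. A site that follows section 7.2 to the letter can therefore randomise someone whom sections 5.2 and 8.4 say must not be randomised.

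Two things are at stake. One is whether a safety exclusion works as an entry criterion. The other is the analysis set: a subject found ineligible before allocation is a screen failure and leaves no trace in the efficacy data, while one found ineligible after allocation belongs to the ITT population permanently.

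**Working it through.** No arithmetic applies to the main point. The check sets the passages side by side.

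**Order of events at Visit 2 (section 7.2).** Eligibility check 3, randomisation 7, concomitant medications 8, vital signs 10, C-SSRS 12, drug screen 13, first dose 18. The C-SSRS is 12 − 3 = 9 items after the eligibility check and 12 − 7 = 5 items after randomisation, but 18 − 12 = 6 items before the first dose.

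**Could an earlier C-SSRS serve?** One is done at Screening (section 7.1, item 6). It answers the part of exclusion 11 about the 6 months before screening. It cannot answer the baseline part, because Screening may be as early as Day −42. Nor does section 7.2 place the baseline C-SSRS at the separate lumbar puncture visit, since only the MMSE and the lumbar puncture may precede Day 0.

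**What happens to a subject who fails at item 12?**
- Section 7.2 limits a screen failure to someone who does not qualify or who discontinues before randomisation. This subject has already been allocated.
- Section 11.3.1 keeps the subject in the ITT population whether or not dosed.
- Section 11.3.1 also requires a baseline and a post-baseline value for a change-from-baseline analysis. The baseline ADAS-Cog 11 and ADCS-ADL exist (items 4 and 5); a post-baseline value may not.

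**Do the other items after randomisation carry a Visit 2 criterion?**
- *Concomitant medications (8):* partly. Exclusion 9 asks for antidepressant and non-seizure anti-epileptic doses to have been stable for 60 days before enrolment, and section 6.3.1 bans certain classes from Visit 1 onwards. A change since Screening is formally recorded only after allocation.
- *Psychoactive doses in general:* inclusion 12 and section 6.3.1 count back from Screening.
- *Antibiotics:* section 6.3.1 counts back from Screening; exclusion 18 names no visit.
- *Blood pressure (exclusion 7b):* no visit named.
- *Drug screen (exclusion 16g):* tied to Screening.

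Only the C-SSRS has an explicit baseline criterion that depends on a later item.

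**Lumbar puncture.** Section 7.2 lists it at item 2, ahead of the item 3 check, or up to 7 days earlier at a visit that verifies only the MMSE. Footnote 6 wants eligibility confirmed first. The two texts do not match as written.

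**Does anything force randomisation to item 7?** Items 8 to 12 are concomitant medications, examination, vital signs, NPI and C-SSRS. None needs the allocation. The first item that does is dosing at 18.

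**The case against.** The best defence is that the list is soft. It allows departures where feasible, sections 5.2 and 8.4 still govern who may be randomised, and a site may do the C-SSRS first without breaching section 7.2. Visit 2 is scheduled only for subjects already found eligible, so item 3 is a re-check. This stands as a limit on the claim: exclusion 11 can be applied in time by a site that departs from the order. It does not make the listed order right, because a site that follows it exactly can breach section 5.2.

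A reader might infer more than the Protocol supports:
- *Ineligible subjects will be dosed.* This does not follow. The C-SSRS, vital signs and concomitant medications all precede the first dose, and section 8.18 provides for action on suicidal ideation.
- *Vital signs and the drug screen share the defect.* They have no explicit Visit 2 criterion. For medications, nothing stops an investigator asking about new drugs at item 3, which is why that point is only a weaker version.
- *Every such subject is lost to the analysis.* Section 12.13 asks for every effort to complete the Visit 10/Early Termination assessments, which include both co-primary scales. The loss is possible, not certain. Allocation is also double-blind, and the Protocol gives no reason for such removals to differ by arm.
- *Subjects will have a needless lumbar puncture.* Footnote 6 can be read as met by the eligibility established before Visit 2 plus the verified MMSE. The texts need aligning; harm is not shown.

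**Conclusion.** The point holds for the C-SSRS. In the order section 7.2 sets out, the baseline part of exclusion 11 cannot be applied before allocation, which conflicts with sections 5.2 and 8.4. The conclusion assumes that the site follows the list and that baseline means Visit 2. The consequence is a randomised but ineligible subject who stays in the ITT population, perhaps without a post-baseline score. The medication point is weaker and depends on reading enrolment in exclusion 9 as randomisation. The lumbar puncture point is a matter of reconciliation only.

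The number affected cannot be derived from the Protocol. A reader might put a figure on it: if 0.5% to 2% of subjects newly met some exclusion at Visit 2, that would be 573 × 0.005 = 2.9 to 573 × 0.02 = 11.5 subjects. That rate is assumed and covers any exclusion, most of which are not Visit 2 criteria, so it says little about new Type 4 or 5 ideation. Even the upper figure is small beside the planned 10% dropout (573 × 0.10 = 57). The number is probably small, and the case for the change rests on its low cost and on making a stated exclusion enforceable.

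**What to change.** Re-order section 7.2 so that the C-SSRS and concomitant medications are completed on Day 0 before a final eligibility confirmation and randomisation. The simplest way is to leave the MMSE and the three scales where they are and move randomisation, with a final eligibility confirmation, below the C-SSRS. This keeps the cognitive scales early, in line with Visits 5, 7 and 11. The baseline NPI would then also precede allocation.

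Reconcile the position of the lumbar puncture in section 7.2 with Table 1 footnote 6, stating which eligibility confirmation the footnote means and where it falls when the procedure is done at the separate earlier visit.

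The cost is an edit to one visit list and one footnote. Every assessment is already scheduled on Day 0, and no repeat checks at a separate lumbar puncture visit are needed for this purpose. Randomisation simply happens later on the same day.
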